## 9.2 Sample Size and Randomization

Sample size: Intervention = 130 (65 statin: 65 placebo) randomized sample; Analytic sample = 94 (47:47) after 28% drop-out. The expected accrual rate is 5 participants per month across three sites (1.6 participants per site), and the planned recruitment duration

is 3 years. We anticipate that all evaluable participants will have completed all study procedures within 4 years. Power and precision arguments are provided below.

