## 3.0 STUDY DESIGN SUMMARY

This is a Phase II randomized, double-blinded, placebo-controlled clinical trial including 130 patients with cirrhosis diagnosed with HCC recruited from Cedars-Sinai Medical Center (CSMC), Ronald Reagan UCLA Medical Center (UCLA), Northwestern Memorial Hospital (NWU), UCSF Medical Center (UCSF), or Emory University Woodruff Health Sciences Center (EU). We will randomize study participants 1:1 to daily pravastatin 40 mg or placebo, created to be identical in color, consistency, and appearance to pravastatin, for an intervention period of 12 months. We expect to have a final sample of 47 study participants on pravastatin and 47 on placebo after accounting for the competing risk of transplantation or death due to cirrhosis (Figure 3). Evaluations will be taken at baseline and at study visits 1-6. Screening data will be reviewed to determine subject eligibility. Subjects who meet all inclusion criteria and none of the exclusion criteria will be enrolled in the study.

The following treatment regimens will be used:

- Experimental treatment: 40 mg pravastatin (N=65).
- Placebo: (N=65).

Total duration of active participation will be 12 months. Total duration of the study is expected to be 5 years.

[figure not shown]

Figure 3. Study profile for the primary endpoint of time to HCC recurrence

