## 9.3.1 Analysis of Primary Endpoint: TTR

The log-rank test will be carried out to compare the distributions of TTR between placebo and pravastatin groups and the Kaplan-Meier estimators will be presented graphically. Cox proportional hazards model will be fitted to the data where the explanatory variable of interest is the indicator of treatment allocation adjusting for clinical and demographic baseline covariates, including sex. Patients who did not experience HCC recurrence, or receive a liver transplant and are still alive at the end of the study will be right censored. Patients who are transplanted or die before HCC recurrence will be treated as a competing risk. A competing risk model for TTR will be used to estimate the cumulative incidence of TTR using time to transplant or death as a competing risk. The proportional hazards assumption will be tested graphically and analytically, and model diagnostics such as martingale and Schoenfeld residuals will be conducted to assess model adequacy. Violation of the proportional hazards assumption will be addressed by use of time-dependent covariates or extended Cox models. The possibility of collinearity among the explanatory variables will be reduced after careful assessment of the correlation matrix and condition index. Automatic variable selection methods in a multivariable Cox proportional hazards model such as stepwise, backward, and forward will be used as a guideline to identify sets of important predictors and a more rigorous approach based on a 4-step procedure outlined in Collett (2003) will be employed (55). Power. Preliminary data indicate that the 12-month RFS is between 57% and 78% in patients with: 1) Child Pugh A or B cirrhosis, 2) small HCCs (typically meeting Milan criteria) 3) liver directed therapy (typically RFA or resection), and 4) no other interventions (27, 56-59). Therefore, we will assume that the 12-month RFS in the control group is 65%. Assuming a common cumulative incidence of the competing risk events at 12 months of 20% (10% due to liver transplant and 10% due to death), a 42-month accrual time and 15-month follow up time, and 10% drop out, data from 47 patients per group achieve 80% power to detect a hazard ratio of 0.45 using a two-sided log-rank test with a 0.1 level of significance. This is equivalent to detecting a decrease in the 12-month cumulative incidence of disease recurrence from 35% in the control group to 18% in the treatment group, which is clinically meaningful. The choice of a type I error rate of 0.1 is appropriate for a randomized phase II trial since this can serve as a randomized screening design for a nondefinitive comparison of statin vs placebo (reference: Mandrekar and Sargent (2010)). We further assumed that TTR and time to death or transplant are independent and exponentially distributed. Statistical power was based on the formulas in Machin et al. (2008) and Pintilie (2006) and were carried out using PASS version 13 (60, 61).

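### The TTR power statement applies the competing-event loss twice, so the stated 80% at HR 0.45 is not the power of the 130 randomised; on the plan's own model the error is conservative

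*Combined protocol and SAP*

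**What the plan says.** Section 9.2 gives the randomised number, "Sample size: Intervention = 130 (65 statin: 65 placebo) randomized sample", followed by "Analytic sample = 94 (47:47) after 28% drop-out". Section 3.0 describes the smaller number in these words: "final sample of 47 study participants on pravastatin and 47 on placebo after accounting for the competing risk of transplantation or death due to cirrhosis".

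The power paragraph of section 9.3.1 assumes 20% competing events at 12 months, half of them transplants and half deaths. Recruitment and observation enter as "a 42-month accrual time and 15-month follow up time". The conclusion drawn for the primary endpoint reads: "and 10% drop out, data from 47 patients per group achieve 80% power to detect a hazard ratio of 0.45". The test is a two-sided log-rank at 0.10. The paragraph equates this with 12-month recurrence falling from 35% to 18%, under independent exponential times. No power is given for 65 per arm.

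Three further places bear on who is analysed:

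- Section 9.3.1 keeps patients who are transplanted or die before recurrence in the analysis, as competing events.
- Section 2.3 censors patients lost to follow-up at their last evaluable scan and counts events only in the 12-month intervention period.
- The Statistical Methodology entry of the Study Summary restricts the primary analysis to patients with the month-12 scan and blood sample.

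**The concern.** A loss can be handled by shrinking the sample before the power calculation, or by modelling it inside the calculation. Doing both counts it twice. Section 3.0 says transplant and cirrhosis death were already removed in reaching 47, yet section 9.3.1 applies a 20% competing-event incidence to those 47.

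Two things are at stake. The power and detectable effect printed for the primary endpoint are not those of the 130 patients to be enrolled. And a primary analytic sample of 94 suggests that 36 randomised patients (130 − 94) fall outside the TTR analysis, although the analysis described in 9.3.1 and the censoring rule in 2.3 use all of them. Read with the Study Summary, the 94 lends numerical support to an analysis of completers, who are selected by what happened after randomisation.

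**Working it through.** **Step 1: where 47 comes from.** 65 × 0.80 × 0.90 = 46.8, and 130 × 0.72 = 93.6, which round to 47 and 94. The stated 28% equals 1 − 0.80 × 0.90. Adding the losses (30%) would give 65 × 0.70 = 45.5. The documents do not print this split, so it is an inference from a close numerical match.

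**Step 2: inputs from 9.3.1.** 12-month cumulative incidence in controls of 35% (recurrence) and 20% (competing); HR 0.45; accrual R = 42 months, follow-up f = 15 months; drop-out 10%; two-sided alpha 0.10.

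- Total hazard: −ln(1 − 0.55)/12 = 0.0665 per month.
- Recurrence hazard: 0.0665 × 0.35/0.55 = 0.0423. Competing hazard: 0.0665 × 0.20/0.55 = 0.0242.
- Pravastatin recurrence hazard: 0.45 × 0.0423 = 0.0191. Its 12-month cumulative incidence is (0.0191/0.0433) × (1 − e^(−12 × 0.0433)) = 17.8%, matching the plan's 18%.

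**Step 3: formulas.** With λ the total hazard in an arm and λe its recurrence hazard, and uniform accrual:

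- P(event) = (λe/λ) × [1 − (e^(−fλ) − e^(−(R+f)λ))/(Rλ)], which gives 0.558 for control and 0.334 for pravastatin.
- Events D = n per arm × 0.90 × (0.558 + 0.334).
- Power (Schoenfeld form) = Φ(√D × |ln HR|/2 − 1.645).

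**Step 4: reproduce the plan.** With n = 47, D = 37.7 and power = 79.0%, against the stated 80%. Treating drop-out as a constant yearly hazard instead of a flat 10% gives 37.8 events and 79.1%.

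**Step 5: is the 20% inside the stated power?** With no competing risk, 47 per arm give 86.7% with 10% drop-out and 89.7% without. The stated 80% needs the competing risk.

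**Step 6: is the 10% inside it?** With the competing risk but no drop-out, the Schoenfeld form gives 82.6%. The Freedman form, Φ(√D × (1 − HR)/(1 + HR) − 1.645), gives 79.1%. Arithmetic alone does not settle this; the wording of 9.3.1 does list 10% drop-out.

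**Step 7: losses applied once, and the follow-up window.** All rows use HR 0.45 and the Schoenfeld form. Ranges run from a flat 10% drop-out to drop-out as a yearly hazard.

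| Follow-up | n per arm entering | Events | Power |
|---|---|---|---|
| 42 + 15 months | 47 | 37.7–37.8 | 79% |
| 42 + 15 months | 65 | 52.2–52.3 | 89% |
| 12-month window | 47 | 22.4–23.7 | 60–62% |
| 12-month window | 65 | 30.9–32.8 | 72–74% |

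On the 42 + 15-month model, 65 per arm have 80% power at HR 0.51 (the Freedman form gives 86.3% power at HR 0.45), and about 49 per arm entering would suffice for 80% at HR 0.45. In the 12-month rows the event probabilities with flat drop-out are 0.350 and 0.178, so D = 65 × 0.90 × 0.528 = 30.9.

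**The case against.** **The split is not printed.** Section 9.2 calls the whole 28% drop-out, section 3.0 attributes the fall to 47 only to transplant and cirrhosis death, and Figure 3, which might show the split, is not available here. This stands for the 10%: its double use is a reading of 9.3.1 plus an inference. It does not rescue the 20%, which section 3.0 says has been removed and which the stated power requires.

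**The formula variant is not named.** Section 9.3.1 cites two formula sources and a software package. A reader might infer that the 80% can be reproduced only with both losses applied to 47. The Freedman result without drop-out (79.1%) shows that this is too strong.

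**The error is on the safe side.** This stands. A reader might infer that the double subtraction leaves the trial underpowered. On the plan's own model it does the opposite.

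**The 94 has a basis in the plan.** The Study Summary's completer rule would produce a smaller analysis set. That explains the number but does not justify it for TTR, because it contradicts the competing-risk and censoring analysis in 9.3.1 and 2.3. It does mean that editing only sections 3.0, 9.2 and 9.3.1 would leave the contradiction in place.

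**47 per arm is sensible elsewhere.** For the 12-month changes in stiffness, fat fraction and biomarkers in section 9.3.2, patients without a month-12 measurement do drop out. This also stands.

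**Conclusion.** The point holds as a conservative error in the stated design, and it should be corrected. Competing events are used both to reach 47 per arm and again in the power for 47 per arm; drop-out probably is too. On the plan's own 42 + 15-month exponential model, the 130 randomised have about 89% power at HR 0.45, against the 80% printed, or 80% power at HR 0.51.

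A reader might infer that the trial therefore has power to spare. The documents do not support that. The 89% depends on counting events over as much as 42 + 15 = 57 months, whereas section 2.3 limits the endpoint to 12 months. On that window, with losses applied once, 65 per arm give 72–74%, below the 80% target. That shortfall comes from the follow-up assumption and not from the double subtraction, but the two have to be settled together before any power can be quoted for 130 patients.

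The results assume exponential times, uniform accrual and the plan's 35%, 20% and 10% inputs.

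**What to change.** - In sections 3.0, 9.2 and 9.3.1, base the TTR power on the 65 per arm randomised, with competing events and drop-out applied once, inside the calculation.
- State the follow-up window that the endpoint definition allows, name the formula used, and restate the power and detectable HR on that window.
- Remove 94 as the size of the primary TTR analysis, and set out how the 28% was obtained.
- Bring the completer wording in the Study Summary into line with the analysis of all randomised patients, using the competing-risk handling of 9.3.1 and the censoring of 2.3.
- Keep 47 per arm as the expected number with 12-month measurements for the change endpoints in 9.3.2, labelled as such.

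The cost is one recalculation and edits to four places in the text. Enrolment does not change.

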## 9.3 Study Endpoints

We have set our primary endpoint as TTR. Secondary endpoints include RFS, OS, waitlist survival, liver stiffness, and circulating biomarkers. Differences in secondary endpoints from baseline to 12-month follow-up will be compared in the pravastatin and placebo groups using a similar approach to the main endpoint.

## 9.3.1 Analysis of Primary Endpoint: TTR

The log-rank test will be carried out to compare the distributions of TTR between placebo and pravastatin groups and the Kaplan-Meier estimators will be presented graphically. Cox proportional hazards model will be fitted to the data where the explanatory variable of interest is the indicator of treatment allocation adjusting for clinical and demographic baseline covariates, including sex. Patients who did not experience HCC recurrence, or receive a liver transplant and are still alive at the end of the study will be right censored. Patients who are transplanted or die before HCC recurrence will be treated as a competing risk. A competing risk model for TTR will be used to estimate the cumulative incidence of TTR using time to transplant or death as a competing risk. The proportional hazards assumption will be tested graphically and analytically, and model diagnostics such as martingale and Schoenfeld residuals will be conducted to assess model adequacy. Violation of the proportional hazards assumption will be addressed by use of time-dependent covariates or extended Cox models. The possibility of collinearity among the explanatory variables will be reduced after careful assessment of the correlation matrix and condition index. Automatic variable selection methods in a multivariable Cox proportional hazards model such as stepwise, backward, and forward will be used as a guideline to identify sets of important predictors and a more rigorous approach based on a 4-step procedure outlined in Collett (2003) will be employed (55). Power. Preliminary data indicate that the 12-month RFS is between 57% and 78% in patients with: 1) Child Pugh A or B cirrhosis, 2) small HCCs (typically meeting Milan criteria) 3) liver directed therapy (typically RFA or resection), and 4) no other interventions (27, 56-59). Therefore, we will assume that the 12-month RFS in the control group is 65%. Assuming a common cumulative incidence of the competing risk events at 12 months of 20% (10% due to liver transplant and 10% due to death), a 42-month accrual time and 15-month follow up time, and 10% drop out, data from 47 patients per group achieve 80% power to detect a hazard ratio of 0.45 using a two-sided log-rank test with a 0.1 level of significance. This is equivalent to detecting a decrease in the 12-month cumulative incidence of disease recurrence from 35% in the control group to 18% in the treatment group, which is clinically meaningful. The choice of a type I error rate of 0.1 is appropriate for a randomized phase II trial since this can serve as a randomized screening design for a nondefinitive comparison of statin vs placebo (reference: Mandrekar and Sargent (2010)). We further assumed that TTR and time to death or transplant are independent and exponentially distributed. Statistical power was based on the formulas in Machin et al. (2008) and Pintilie (2006) and were carried out using PASS version 13 (60, 61).

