## • Primary Efficacy Endpoint

Following the American Association for the Study of Liver Diseases-Journal of the National Cancer Institute guidelines for trial design in HCC, we have set our primary endpoint as TTR, according to the recommendation for Phase II studies that assess adjuvant therapies secondary to liver directed therapy (33). TTR will be defined as the time from randomization to the first occurrence of a documented HCC recurrence or HCC death, within the 12-month intervention and assessment period. Participants who experience death attributed to their underlying liver cirrhosis, or other cause, will be censored at death date. For participants who do not recur or die and are lost to follow-up prior to the 12-month study visit, analysis of TTR will be censored at their last date of evaluable scan before drop-out.

In this study, we will rely heavily on the mRECIST outcome guidelines and the Liver Imaging Reporting and Data System (LI-RADS) diagnostic algorithm for defining hepatic recurrence (34, 35), and central expert independent radiographic review by MedQIA.

Pathological Definition: Participants who receive a transplant will become ineligible at the time of transplantation. Recurrent HCCs may also be identified at time of transplantation during the examination of the explant by a pathologist. These "incidental" HCCs represent a sizable proportion, amounting to 22% of HCCs among those receiving a liver transplant. Thus, if transplantation occurs and a pathologically confirmed HCC is detected, we will examine these pathologically defined tumors as a **secondary** definition of recurrence.

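### The only outcome plot named for TTR is Kaplan-Meier, which, if transplant and death are censored, shows net risk and overstates the probability of recurrence that the plan's 35% vs 18% target describes.

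*Combined protocol and SAP*

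**What the plan says.** Section 9.3.1 plans a log-rank test of TTR and states that "the Kaplan-Meier estimators will be presented graphically". The only other graphical item there is a check of proportional hazards.

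On events that preclude recurrence, the section says: "Patients who are transplanted or die before HCC recurrence will be treated as a competing risk". It continues, with the last word left off here: "A competing risk model for TTR will be used to estimate the cumulative incidence of TTR using time to transplant or death as a competing". No plot of that estimate is mentioned.

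Section 2.3 (Primary Efficacy Endpoint) defines a TTR event as the "first occurrence of a documented HCC recurrence or HCC death, within the 12-month intervention and assessment period". On other deaths it says: "Participants who experience death attributed to their underlying liver cirrhosis, or other cause, will be censored at death date". Transplanted participants become ineligible at transplantation; whether the curve censors them is not stated.

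For planning, section 9.3.1 says "we will assume that the 12-month RFS in the control group is 65"%. It assumes a "common cumulative incidence of the competing risk events at 12 months of 20% (10% due to liver transplant and 10% due to death"), the same in both arms, a hazard ratio of 0.45, and independent exponential times. It expresses the target as a fall in the 12-month cumulative incidence of recurrence from 35% to 18%.

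**The concern.** A Kaplan-Meier curve that censors transplant and death estimates how many patients would recur if neither could happen first. Cumulative incidence is the share of randomized patients who actually recur, given that some are transplanted or die first. With a fifth of patients expected to have a competing event by month 12, the two differ visibly.

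The plan states its target as a cumulative incidence but specifies a figure on the other scale. A reader who takes 12-month recurrence from the figure would read both arms, and the absolute benefit, too high against the 35% vs 18% target. Nor does the plan say whether the 12-month rates to be quoted come from the curve or from the competing-risk model, so the choice could be made after results are seen.

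**Working it through.** **Inputs (section 9.3.1).** Control recurrence 35% and competing events 20% at 12 months; hazard ratio 0.45; 47 per arm; two-sided alpha 0.10; "a 42-month accrual time and 15-month follow up time, and 10% drop out"; independent exponentials.

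**Step 1: 12-month cumulative hazards, control.** Let H1 be recurrence and H2 the competing events.
- H1 + H2 = -ln(1 - 0.35 - 0.20) = 0.7985
- H1 = (35/55) × 0.7985 = 0.508
- H2 = (20/55) × 0.7985 = 0.290

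On pravastatin, H1 = 0.45 × 0.508 = 0.229, with H2 unchanged.

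**Step 2: reproduce the plan's figures.**
- Cumulative incidence = H1/(H1 + H2) × [1 - exp(-(H1 + H2))]. On pravastatin: 0.229/0.519 × (1 - exp(-0.519)) = 17.8%, against the stated 18%.
- Power: uniform accrual over 42 months, 15 further months and exponential dropout of 10% per 12 months (my reading of the 10%) give 37.8 events. By Schoenfeld's formula, sqrt(37.8/4) × |ln 0.45| - 1.645 = 0.81, a power of 0.791 against the stated 80%.

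This event count includes recurrences after month 12, whereas section 2.3 limits TTR to 12 months. That is a separate sample-size matter and does not enter the 12-month comparison below.

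**Step 3: what the Kaplan-Meier plot would show with competing events censored.** 1-KM = 1 - exp(-H1).
- Control: 1 - exp(-0.508) = 39.8%, against 35.0%.
- Pravastatin: 1 - exp(-0.229) = 20.4%, against 17.8%.
- Difference between arms: 39.8 - 20.4 = 19.4 points, against 35.0 - 17.8 = 17.2.

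A simulation of 400,000 patients per arm, with Kaplan-Meier computed directly, gave 39.9% vs 35.1% and 20.4% vs 17.8%.

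**Step 4: other readings of the inputs.** The 35% comes from an assumed RFS of 65%, which might be a net quantity; then H1 = -ln 0.65 = 0.431. The 20% may be net (H2 = -ln 0.80 = 0.223) or a cumulative incidence (H2 = 0.279). Separately, HCC deaths are TTR events in section 2.3, so fewer than 20% may compete. As a lower illustration, let only the 10% transplant share compete: H1 + H2 = -ln(0.55) = 0.598, split 35:10. Gaps are taken before rounding.

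| Reading | Control: 1-KM vs cumulative incidence | Gap | Pravastatin: 1-KM vs cumulative incidence | Gap |
|---|---|---|---|---|
| 35% and 20% both cumulative incidences | 39.8% vs 35.0% | 4.8 | 20.4% vs 17.8% | 2.6 |
| 35% net, 20% cumulative incidence | 35.0% vs 30.8% | 4.2 | 17.6% vs 15.4% | 2.2 |
| 35% and 20% both net | 35.0% vs 31.6% | 3.4 | 17.6% vs 15.9% | 1.8 |
| 35% cumulative incidence, only transplant (10%) competes | 37.2% vs 35.0% | 2.2 | 18.9% vs 17.7% | 1.2 |

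The direction is the same in every row. The stated 18% does not settle which reading was meant, since both 17.8% and 17.6% round to it; the plan's own label is cumulative incidence.

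**The case against.** The strongest reply is that section 9.3.1 already plans the competing-risk estimate, so the right quantity will be produced. That stands and narrows the point to the figure. A reader might infer that the report will carry two conflicting 12-month rates per arm. The documents do not say that rates will be read from the Kaplan-Meier curve, or that no other figure will be drawn; they leave both open.

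A second reply is that Kaplan-Meier is not wrong in itself. Under the plan's independence assumption it validly estimates net risk, it is the usual companion to the log-rank test, and it follows section 2.3 for non-HCC deaths. This also stands: the overstatement arises only when the curve is read as the actual probability of recurrence. Independence, however, is assumed only for the power calculation. Section 1.3 gives reason to doubt it, because it links recurrence and progression to loss of transplant candidacy.

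Third, the effect is small. The distortion of the difference is at most 19.4 - 17.2 = 2.2 points, while with 47 per arm its binomial standard error is sqrt(0.35 × 0.65/47 + 0.18 × 0.82/47), about 8.9 points. Relative inflation is similar in both arms (39.8/35.0 = 1.14; 20.4/17.8 = 1.15), so the relative contrast hardly moves. This supports treating the point as an improvement in reporting.

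**Conclusion.** The point holds as a matter of presentation. The one outcome plot named for the primary endpoint is not on the scale of the target. At 12 months it would overstate recurrence by up to 4.8 points in control and 2.6 on pravastatin; by about 3.4-4.2 and 1.8-2.2 if 35% is net risk; and by less if HCC deaths count as TTR events (2.2 and 1.2 if only transplant competes and 35% is a cumulative incidence). This rests on exponential, independent times and on competing events being censored in the curve, which section 2.3 states for non-HCC deaths and which is inferred for transplant.

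A reader might infer that the primary analysis is biased. It is not, on this ground: with competing events censored, the log-rank test and Cox model compare cause-specific hazards, and neither they nor the power depend on which curve is drawn. Nor should one infer that Kaplan-Meier is free of the issue for OS, since section 9.3.2 treats transplant as a competing risk there.

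**What to change.** In section 9.3.1:
- Make non-parametric (Aalen-Johansen) cumulative incidence curves by arm the primary TTR figure, one set for recurrence and one for transplant/death, and take the 12-month rates and confidence intervals from them.
- Keep the log-rank test, described as a test of the cause-specific hazard.
- Make any Kaplan-Meier plot of TTR supplementary, labelled as net risk, and state how it handles transplant and death.

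In the same edit, reconcile section 2.3 (non-HCC death censored, HCC death an event) with section 9.3.1 (death before recurrence a competing risk). Until that is done, it is undefined which deaths the new curves count as competing.

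The cost is SAP wording and standard software. No new data are needed, and the plotting change alters neither the test nor the sample size.

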#### • Secondary Efficacy Endpoints

Secondary endpoints include recurrence-free survival (RFS), overall survival (OS), waitlist survival, liver stiffness, liver fat fraction, circulating biomarkers, and liver tissue biomarkers. Differences in secondary endpoints will be compared in the pravastatin and placebo groups.

1) RFS: We will assess the effect of pravastatin on RFS. RFS will be defined as the time from randomization to the first occurrence of a documented HCC recurrence, within the 12-month intervention and assessment period.

2) OS: We will examine the effect of pravastatin on OS (defined as the time from randomization to death from any cause).

3) Waitlist drop-off: We will evaluate the effect of pravastatin on reducing waitlist dropout due to any of the following causes: 1) HCC progression outside of Milan/T2 criteria, 2) cirrhosis progression (too sick to transplant), or 3) death.

Participants who are delisted for other reasons (such as positive alcohol test) will be censored at date of delisting.

4) Change in liver stiffness: We will evaluate the effect of pravastatin on withinperson change in liver stiffness, as measured by magnetic resonance elastography (MRE) or FibroScan, between Study Visit 1 (0 month) and Visit 6 (12 month). Within-patient consistency is required between Study Visits 1 and 6 with regards to liver stiffness testing modality (MRE or FibroScan).

5) Change in liver fat fraction: We will evaluate the effect of pravastatin on withinperson change in liver fat fraction, as measured by MRI-proton density fat fraction (PDFF), between Study Visit 1 (0 month) and Visit 6 (12 month).

6) Change in serum biomarkers of monocyte/macrophage and stellate cell activation: We will examine the effect of pravastatin on change in serum biomarkers including cytokines, chemokines, soluble receptors, and proteins (specifically, IL6, TNF $\alpha$ , sTNFRII, IL18BP, sCD163, IL10, IL17, IL-8, CCL17, TGF $\beta$ ).

7) Levels of liver tissue markers related to HCC: We will examine the effect of pravastatin on levels of liver tissue markers related to HCC including those in the Wnt/ $\beta$ -catenin pathway (specifically,  $\beta$ -catenin and glutamine synthetase).

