# 9.3.2 Analysis of Secondary Endpoints RFS and OS

For the secondary objective, comparison of overall survival and recurrence free survival between the pravastatin and placebo groups will be achieved by fitting a Cox proportional hazards model as described above for TTR. In this analysis, a competing risk model will

be fitted to the data using time to transplant only as a competing risk since overall survival includes death from any cause.

**Waitlist drop-off.** Fischer's exact test will be used to compare the proportions of patients on the waitlist who drop off between the pravastatin and placebo group. We expect about 35% of patients in the placebo group to drop off due to various causes such as death and HCC progression beyond Milan. Data from 47 patients per group achieve 80% power to detect a decrease in drop-off rates from 35% in the control group to 14% in the treatment group using a one-sided Fisher's exact test at the 0.1 level of significance.

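### Section 2.3 defines recurrence-free survival without death, while 9.3.2 gives it a competing-risk model justified only for overall survival; a smaller gap affects HCC deaths in TTR

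*Combined protocol and SAP*

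**What the plan says.** **RFS.** Section 2.3 (Secondary Efficacy Endpoints) states that "RFS will be defined as the time from randomization to the first occurrence of a documented HCC recurrence", within the 12-month intervention and assessment period. Death is not part of the definition. The next item, OS, counts death from any cause. Section 9.3.2 analyses RFS and OS together by "fitting a Cox proportional hazards model as described above for TTR". It then specifies a competing-risk model "using time to transplant only as a competing risk since overall survival includes death from any cause".

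**TTR.** Section 2.3 (Primary Efficacy Endpoint) defines TTR as "the time from randomization to the first occurrence of a documented HCC recurrence or HCC death". It adds: "Participants who experience death attributed to their underlying liver cirrhosis, or other cause, will be censored at death date". Section 9.3.1 says: "Patients who are transplanted or die before HCC recurrence will be treated as a competing risk". Its cumulative-incidence model uses transplant or death as the competing event, without distinguishing causes of death. Section 3.0, describing the sample expected for the primary endpoint, names the competing risks as transplant and death from cirrhosis.

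**Planning figures.** The power paragraph in 9.3.1 assumes a control 12-month RFS of 65% and a 20% incidence of competing events at 12 months, half transplant and half death. It assumes independent exponential times. The target is a "decrease in the 12-month cumulative incidence of disease recurrence from 35% in the control group to 18% in the treatment group", with a hazard ratio of 0.45.

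**The concern.** For RFS, the definition and the model do not describe the same endpoint. The reason given for leaving death out of the competing events is that death is already an event. That holds for OS and does not hold for RFS under 2.3. Three treatments of a death before recurrence are then open:

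- censored (2.3 and 9.3.2 read literally);
- competing (9.3.2 refers back to the TTR method, where death competes);
- counted as an event (what the transplant-only rule would imply if RFS was meant to include death).

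If 2.3 is followed, the reported figure overstates the share of patients alive without recurrence. The hazard ratio also looks stronger than one that counts death, unless pravastatin lowers death as much as recurrence. The hypotheses in Section 1.3 include better overall survival but give no size. Leaving the choice open also means that it could be made after results are seen.

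For TTR, one type of patient is affected in the log-rank and cause-specific Cox analyses: someone who dies of HCC with no documented recurrence before death. That patient is an event under 2.3 and a competing event under 9.3.1 as worded.

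**Working it through.** **Inputs (9.3.1, control group, 12 months):** recurrence 35%, death 10%, transplant 10%, exponential times. The treatment hazard ratio on recurrence is 0.45.

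**Step 1. Hazards.** The chance of being free of all three events at 12 months is 1 − 0.55 = 0.45.
- Total hazard = −ln(0.45)/12 = 0.06654 per month.
- Split 35:10:10, this gives recurrence 0.04235, death 0.01210 and transplant 0.01210.

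**Step 2. Reproduce the plan's own contrast.** The treated recurrence hazard is 0.45 × 0.04235 = 0.01906, with death and transplant unchanged at 0.02420 together, so the total is 0.04325. Cumulative incidence of recurrence at 12 months = (0.01906/0.04325) × (1 − exp(−0.04325 × 12)) = 0.4406 × 0.4049 = 0.178. This matches the stated fall from 35% to 18%, so the hazards agree with the plan.

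**Step 3. Control 12-month RFS under each treatment of death.** Here RFS is one minus the cumulative incidence of the RFS event, with transplant always competing.

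| Death before recurrence | Calculation | 12-month RFS |
|---|---|---|
| Censored | 1 − (0.04235/0.05444) × (1 − exp(−0.05444 × 12)) | 62.7% |
| Competing | 1 − 0.35 | 65.0% |
| Counted as an event | 1 − (0.35 + 0.10) | 55.0% |

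The Kaplan-Meier version, with transplant censored, shows the same gap: exp(−0.04235 × 12) = 60.2% with deaths censored, against exp(−0.05444 × 12) = 52.0% with deaths counted.

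**Step 4. RFS hazard ratio.** As defined in 2.3 it is the recurrence hazard ratio, 0.45. With death counted and a hazard ratio h on death, it is (0.45 × 0.04235 + h × 0.01210)/0.05444. The documents give no h, so these values are assumptions:
- h = 1 (no effect on death): 0.57
- h = 0.70: 0.51
- h = 0.45 (same effect as on recurrence): 0.45

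**Step 5. TTR, passages compared.**
- Death from cirrhosis or another cause: censored in 2.3, competing in 9.3.1. The log-rank and cause-specific Cox analyses treat these alike. Only the cumulative-incidence estimate depends on the difference.
- HCC death without prior documented recurrence: an event in 2.3, competing in 9.3.1. This is a real difference in all the analyses. The documents give no rate for it, so no size is calculated.

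**The case against.** **TTR.** A reader might infer that the primary endpoint has two rival event sets. The documents do not support going that far. Section 3.0 names death due to cirrhosis, not any death, alongside transplant as the competing risk for the primary endpoint. That agrees with 2.3 and suggests that death in 9.3.1 is shorthand for non-HCC death. MRI or CT surveillance at months 3, 6, 9 and 12 (Study Schema) should also make HCC death without prior documented recurrence uncommon. What stands is that 9.3.1 as worded has no exception for HCC death.

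**Power.** A reader might also infer that the stated 80% power is wrong because it does not match the 2.3 event. That does not follow. The documents do not say what share of the 10% deaths are HCC deaths, and under the Section 3.0 reading the share is zero. Any recalculation would need an assumed share and an assumed effect on HCC death. It would also have to apply the 12-month window in 2.3, which differs from the accrual and follow-up times in the power paragraph. No revised power is claimed here.

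**RFS.** The analysts might count death in RFS anyway, as the name suggests and the transplant-only rule allows. The overstatement would then vanish. But 2.3 says otherwise, and 9.3.2 refers back to a method in which death competes. Limiting the reason in 9.3.2 to OS, and making death a competing event for RFS, would also reconcile the text. It would leave an endpoint called recurrence-free survival that ignores death. RFS is one of seven secondary endpoints in a phase II trial that the plan calls nondefinitive, which limits the weight of the point but does not remove it.

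**Conclusion.** The RFS inconsistency is confirmed and is the main point. The definition in 2.3 omits death, the reason in 9.3.2 fits OS only, and the role of a death before recurrence in RFS is not settled. On the plan's control inputs, following 2.3 gives a 12-month RFS 8 to 10 percentage points above one that counts death (62.7% or 65.0%, against 55.0%). The RFS hazard ratio is 0.45 as defined, against 0.57 with death counted and unaffected by treatment. These figures rest on the plan's rates and exponential assumption; the 0.57 and 0.51 also rest on assumed effects on death. It cannot be said that the reported RFS will be overstated, because the text does not settle which treatment would be used.

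The TTR point is minor: a missing exception for HCC death in 9.3.1, with an unknown and possibly small number of patients affected. Both should be corrected before unblinding.

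**What to change.** 1. **Section 2.3, RFS.** Define RFS as time from randomisation to first documented recurrence or death from any cause. The transplant-only model in 9.3.2 then fits both RFS and OS, and its reason should name both.
2. **Section 9.3.1, TTR.** State that the event is documented recurrence or HCC death. State that transplant and non-HCC death are censored in the log-rank and cause-specific Cox analyses and are competing events in the cumulative-incidence analysis. This agrees with 2.3 and 3.0.
3. **Section 9.3.1, power paragraph.** Replace the 65% control RFS assumption with a control 12-month cumulative incidence of recurrence of 35%, a figure that the paragraph already uses. Left as it is, the 65% would conflict with the new RFS definition, which gives 55% on the same inputs. Label the 10% death as non-HCC death; the sponsor should confirm that this is what was meant.

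The cost is wording in three sections and one confirmation by the study team. No new data are needed, because date and cause of death are already required for TTR and OS under 2.3.
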